Smart Telehealth Exercise Intervention to Reduce COPD Readmissions

Study Protocol & Statistical Analysis Plan

NCT03089853

March 19, 2020

[name]., Principal Investigator
University of Alabama at Birmingham
Birmingham, AL 35294

We have designed a prospective *randomized controlled* study comparing an early NMES and telehealth remote pulmonary rehabilitation intervention with usual care to determine the impact on respiratory morbidity and also to investigate the mechanisms of such benefit. The primary outcome is the rate of all-cause readmissions within 30 days following an index hospitalization for COPD exacerbation. Secondary outcomes will include change in dyspnea, functional capacity, COPD disease activity and respiratory quality of life, and also changes in skeletal muscle and systemic inflammation.

Sample Size Calculation and Statistical Considerations: We propose enrolling a sample size of convenience of 30 participants randomized to intervention and usual care. We will use the observed effects size for the primary outcome of 30-day readmission to design a larger clinical trial. Standard deviations of measures of secondary outcomes will aid sample size calculations for Specific Aims 2 and 3. Comparisons between groups will be made for continuous variables using independent t-test or Mann-Whitney U-test for non-parametric data, and using chi-square or Fisher's exact test for categorical variables. Comparisons will be deemed to be statistically significant at a two-tailed alpha of 0.05 or less. Multivariable regression models will be created to assess association between the intervention and change in systemic inflammation and other measures such as functional capacity and quality of life indices, as well as muscle biopsy measures. The results of this pilot study will inform sample size for each Aim for a large mechanistic multicenter randomized controlled trial.

Subjects: Consecutive patients admitted to the general medicine or pulmonary floors with a primary diagnosis of acute exacerbation of COPD will be eligible for the study. Subjects will be enrolled within the first 36 hours of admission after written informed consent from the subject. Those with a secondary diagnosis of congestive heart failure and other respiratory conditions that could confound the diagnosis such as pneumonia, bronchiectasis and lung cancer will be excluded. In addition, those on invasive or noninvasive mechanical ventilation will not be enrolled. Participants with pacemakers/defibrillators will not be enrolled due to concern for interaction with NMES.

Protocol/Intervention: Subjects with spirometry proven COPD and hospitalized for an acute exacerbation will be randomized in a 1:1 ratio to either receive remote tele pulmonary rehabilitation intervention or usual care. Usual care will consist of a protocolized regimen of 5 days of systemic steroids, unless the treating physician determines a different regimen, in which case the change will be documented. *NMES training protocol:* Bipolar self-adhesive neuromuscular stimulation electrodes will be placed over the distal-medial and proximal-lateral portion of the quadriceps femoris muscle group. Stimulation pulses (30 Hz trains of 300 μ sec biphasic pulses) will be delivered using a Respond II neuromuscular electrical stimulator (Medtronic, San Diego, CA). A 5 sec on/25 sec off work/rest ratio will be used initially, progressing to 10 sec on/30 sec off, as described by Neder.¹⁸ The patient will be fully supported while knee extensions are performed as the participant sits in a chair. Current from the stimulator will be manually increased and determined by patient tolerance. The goal for each patient will be to reach the highest tolerable amplitude (up to 100mA). Training will be performed on each quadriceps femoris muscle, 30 minutes/day, for 2 weeks including hospital stay till return to the COPD Clinic at which time participants will return the NMES equipment. *Remote Telehealth Intervention protocol:* On return to clinic for follow-up, patients will be initiated on remote telehealth pulmonary rehabilitation at home via a data enabled smart phone with video capabilities facilitating two-way conferencing, according to a standardized regimen for a total of 12 weeks. Safety will be monitored by also providing automatic sphygmomanometers to measure blood pressure before and after exercise, as well as heart rate and oxygen saturation assessments using a pulse oximeter. Exercise regimens will be prescribed thrice a week according to standard pulmonary rehabilitation guidelines.⁶⁶ Exercise sessions will include aerobic exercises, resistance training and breathing training techniques. Regimens will be individualized according to patients' baseline exercise tolerance as determined by initial six minute walk distance as well as their subjective sense of dyspnea. The study will have 3 aims as follows:

Aim 1: To determine if an NMES and remote tele pulmonary rehabilitation intervention reduces 30-day all cause readmissions in patients hospitalized for acute exacerbation of COPD. All COPD patients hospitalized for an acute exacerbation will be enrolled in an ongoing comprehensive COPD care management intervention, and will be evaluated by a nurse or nurse practitioner in addition to the treating physician, and treated using a standardized order set which includes delivering a uniform duration of five days of antibiotics and systemic steroids. All participants will receive standardized care that includes educational material that encompasses general information about COPD, medications, and red flag symptoms; tobacco cessation counseling for smokers; short interval follow-up at 2 weeks at the COPD Clinic; monthly follow-up at the COPD Clinic; and regular phone calls by a registered nurse to enquire about symptoms as well as to address compliance with inhalers, smoking cessation, physical activity, nutrition, vaccines and coping with a chronic health condition. These calls will be made daily for 2 weeks and then weekly for 3 months. Deterioration in a patient's symptoms will be relayed to physicians for appropriate action. **Measurements:** Exacerbations and hospitalizations will be recorded.

Aim 2: To evaluate the effects of an NMES and remote tele pulmonary rehabilitation intervention on muscle strength, dyspnea and respiratory quality of life in COPD post hospital discharge. Pre and post intervention measurements will be made comparing assessments at 14 days at the time of COPD Clinic visit with assessments at 12 weeks on completion of the intervention. These measurements will be made in both intervention and control arms. **Instruments of Measurement:** (a) Muscle strength of quadriceps using a dynamometer (b) The 30-Second Chair Stand Test to assess skeletal muscle dysfunction, leg strength and endurance (c) Functional capacity using the six minute walk test (d) Physical activity using the Modified Baecke Questionnaire for Older Adults (e) Dyspnea using the San Diego Shortness of Breath Questionnaire and the modified Medical Research Council scores (f) COPD related Quality of life using the COPD Assessment Test (g) Forced expiratory volume in the first second (FEV₁) and (h) Psychosocial Risk Factor Survey (PRFS) to measure the primary psychosocial risk factors of depression, anxiety, anger/hostility, emotional guardedness and social isolation.

Aim 3: To evaluate the effects of NMES and remote tele pulmonary rehabilitation intervention on systemic and muscle inflammation. Pre- and post- intervention assessments will be made of muscle and systemic inflammation at admission and at 4 weeks. **Instruments of Measurement:** (a) Muscle biopsy of the vastus lateralis muscle: Briefly, biopsies will be performed under local anesthetic (1% Lidocaine) using a 5 mm Bergstrom type biopsy needle under suction. Approximately 50-70 mg of muscle for immunohistochemistry will be mounted cross-sectionally and frozen in liquid nitrogen-cooled isopentane. Remaining tissue will be snap frozen in ~30 mg portions for biochemical assays. Myofiber type distribution will be assessed using myosin heavy chain (MHC) isoform immunofluorescence microscopy, muscle bioenergetics in response to oxidative stress, and protein cell signaling of the IL-6/STAT3 and TNF-alpha/NF-KB pathways by immunoblotting of muscle tissue protein lysate; (b) Systemic inflammation as assessed by serum C-reactive protein (CRP), serum fibrinogen, plasma TNF- α and plasma interleukin 6.

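### The readmission effect observed in about 15 patients per arm is too imprecise to serve as the planning effect for the larger trial

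*Combined protocol and SAP*

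**What the plan says.** The opening design paragraph defines the endpoint: "The primary outcome is the rate of all-cause readmissions within 30 days following an index hospitalization for COPD exacerbation". The section Sample Size Calculation and Statistical Considerations fixes the size: "We propose enrolling a sample size of convenience of 30 participants randomized to intervention and usual care". Protocol/Intervention gives 1:1 allocation ("will be randomized in a 1:1 ratio to either receive remote tele pulmonary rehabilitation intervention or usual care"), so about 15 per arm.

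The same statistical section then states what the primary result is for: "We will use the observed effects size for the primary outcome of 30-day readmission to design a larger clinical trial". The next sentence treats the other aims differently: "Standard deviations of measures of secondary outcomes will aid sample size calculations for Specific Aims 2 and 3". The section closes more loosely: "The results of this pilot study will inform sample size for each Aim for a large mechanistic multicenter randomized controlled trial".

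No control readmission rate, target difference, power, confidence interval or shrinkage is given for either trial. For a proportion, the only listed analysis is a chi-square or Fisher's exact comparison, with "Comparisons will be deemed to be statistically significant at a two-tailed alpha of 0.05 or less".

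**The concern.** For Aims 2 and 3 the plan carries forward standard deviations, which are nuisance parameters that a pilot can reasonably supply. For the primary outcome it carries forward the effect itself. With 15 per arm, one readmission moves an arm's rate by 1/15 = 6.7 points, and required sample size varies roughly with the inverse square of the difference. Small chance shifts in the pilot therefore become very large shifts in the successor's size.

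The risk difference is unbiased before any selection. A superiority sample size, however, can be computed only when the pilot happens to favour the intervention, and a favourable pilot that overstates the effect yields a trial that is too small. Sizing a successor is a stated purpose of this study, so the weakness affects something the pilot is meant to deliver.

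**Working it through.** **The plan's own figure.** The 30 is declared a convenience number. No rate, effect or power lies behind it, so there is nothing to reproduce, and the number itself is not criticised.

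**Inputs from the documents.** 30 patients, 1:1, hence 15 per arm; two-sided 0.05 (stated for the pilot and assumed for the successor).

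**Assumed inputs.** One binary outcome per patient, no dropout, successor power 80%, and nine pairs of true rates with control 20–40% and reductions of 10–20 points.

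**Precision.** Half-width = 1.96 × √{[p₁(1−p₁) + p₂(1−p₂)]/15}. At 20% v 10% this is 1.96 × √{(0.16 + 0.09)/15} = 1.96 × 0.129 = 25.3 points, which is 2.5 times the 10-point effect.

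**Sensitivity to one event.** N per arm = {1.96√[2p̄(1−p̄)] + 0.84√[p₁(1−p₁) + p₂(1−p₂)]}² / (p₁−p₂)², where p̄ is the mean of the two rates; calculated with unrounded normal quantiles and rounded up.

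- 3/15 v 1/15: (0.942 + 0.397)² / 0.1333² = 1.793/0.01778, so 101 per arm. Newcombe 95% CI for the difference: −13 to 39 points.
- 3/15 v 2/15: (1.033 + 0.442)² / 0.0667² = 2.175/0.00444, so 490 per arm. Newcombe 95% CI: −21 to 34 points.

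One extra readmission multiplies the successor's size by 490/101 = 4.9, although the two intervals are nearly the same.

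**All possible pilots.** All 16 × 16 outcomes were enumerated with exact binomial probabilities. For each favourable outcome, N was computed from the observed rates, and the power of that N was then found under the true rates.

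| True rates, control/intervention (%) | True need per arm | Half-width ÷ true effect | No benefit seen (%) | N off by more than ×2, if favourable (%) | Mean true power, if favourable (%) |
|---|---|---|---|---|---|
| 20/10 | 199 | 2.5 | 30 | 63 | 51 |
| 25/12.5 | 152 | 2.2 | 26 | 74 | 56 |
| 25/15 | 250 | 2.8 | 32 | 69 | 49 |
| 30/10 | 62 | 1.4 | 12 | 55 | 68 |
| 30/15 | 121 | 2.0 | 22 | 65 | 59.5 |
| 30/20 | 294 | 3.1 | 33 | 79 | 47 |
| 40/20 | 82 | 1.6 | 15 | 62 | 65 |
| 40/25 | 152 | 2.2 | 24 | 65 | 57 |
| 40/30 | 356 | 3.4 | 35 | 80 | 45 |

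Among favourable pilots, 31–62% give an N less than half the true need and 11–26.5% give one more than twice it. Over all pilots, only 13–40% give an N within a factor of 2.

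**If readmissions are counted instead.** The endpoint is worded as a rate, so repeat readmissions might count. With Poisson counts at the same mean rates and N per arm = (1.96 + 0.84)² × (r₁ + r₂)/(r₁ − r₂)², the half-width is 28–42 points. There is no N in 15–38% of pilots; among the rest, 54–80% are off by more than a factor of 2 and mean power is 40–67%. The conclusion does not depend on the binary reading.

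**The case against.** The strongest reply is that the plan gives no formula. Using an effect to design a trial need not mean inserting the point estimate unadjusted, and the closing sentence of the section leaves room for other inputs. The document is short, and the successor's own protocol would be expected to justify its size. The condition stands: the figures apply if the point estimate is the planning effect. That is nonetheless the natural reading, because the effect is named for the primary outcome and only standard deviations for the other aims. The looser closing sentence does not withdraw the specific one.

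It is also fair that this is openly a pilot, that nothing in its conduct changes, and that the percentages belong to assumed rates. The first two limit the severity. The third affects the exact values but not the direction, which is the same for all nine pairs.

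The last objection is that a target difference can be wrong too. If the chosen target is 1.5 times the true effect, N is less than half the true need in 67–100% of pilots, with mean power 44–47%, which is no better than the present plan. If it is two-thirds of the true effect, N is off by more than a factor of 2, almost always too large, in 58–81%, with mean power 95–98%. This stands as a limit on what the fix promises. It does not rescue the present rule: a minimum important difference is not an estimate of the truth, and a trial powered for it is powered for a difference someone has judged worth detecting.

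**Conclusion.** The concern holds, as a minor point. With about 15 per arm, the uncertainty in the readmission difference exceeds the assumed true effect in every case examined. Taken as the planning effect, the estimate would more often than not give a successor whose size is wrong by more than a factor of 2, or no size at all. This rests on reading the observed effect as the planning effect, on assumed rates and 80% power because the documents state none, and on complete follow-up; dropout would widen the intervals. Enrolment, testing and participant safety in this trial are unaffected.

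**What to change.** Replace the sentence on using the observed effect with wording such as:

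> The larger trial will be sized on a prespecified minimum important reduction in 30-day readmission. The pilot between-arm risk difference will be reported with its 95% CI and will not be used as the planning effect. The pilot pooled readmission rate will be carried forward with its 95% CI, and the sample size will be shown over that range.

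Illustration only: with 6 of 30 readmitted (20%, Wilson 95% CI 10–37%) and an assumed 10-point target, the planning rates are 25% v 15% and the need is 250 per arm. Over the CI for the pooled rate, the need runs from 134 to 366.

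The cost is SAP wording, with no extra patients or visits. The downsides are that the investigators must agree on an important difference, that the successor may look larger, and that the pooled rate is itself imprecise: 1.96 × √(0.2 × 0.8/30) = 14 points at 20%, and 16 points at 30%. A lighter edit would meet the core of the concern if the investigators want to keep the pilot effect in view: report it with its 95% CI and state that the successor will not be sized on the point estimate alone.

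### Aim 3: no analysis names the admission value as a covariate; with 30 complete pairs ANCOVA on it costs at most about 4% in variance and, at equal SDs, gains up to 22% over the better unadjusted t-test

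*Combined protocol and SAP*

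**What the plan says.** The section on sample size and statistical considerations gives one rule for all continuous outcomes: "Comparisons between groups will be made for continuous variables using independent t-test or Mann-Whitney U-test for non-parametric data". It then adds a regression: "Multivariable regression models will be created to assess association between the intervention and change in systemic inflammation". That sentence goes on to cover functional capacity, quality of life and the biopsy measures, and lists no covariates for any of them.

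The opening design paragraph words the Aim 3 outcomes as changes: "and also changes in skeletal muscle and systemic inflammation". The Aim 3 section gives the measurement times: "Pre- and post- intervention assessments will be made of muscle and systemic inflammation at admission and at 4 weeks". So every Aim 3 marker is planned to have an admission value.

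On size, the plan states "We propose enrolling a sample size of convenience of 30 participants randomized to intervention and usual care", and Protocol/Intervention says that patients "will be randomized in a 1:1 ratio to either receive remote tele pulmonary rehabilitation intervention or usual care". On what the pilot passes on, it says "Standard deviations of measures of secondary outcomes will aid sample size calculations for Specific Aims 2 and 3", without saying whether this means the SD of the raw value, of the change, or of the residual after adjustment.

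**The concern.** Two things are left open for Aim 3: the variable tested (change or 4-week value) and the covariates in the regression. A t-test on change uses the admission value only by subtracting it, which fixes the slope at 1. A t-test on the 4-week value ignores it. ANCOVA estimates the slope from the data.

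Which unadjusted test is more precise depends on the correlation between the two measurements, which the documents do not give. With about 15 patients per arm, a poor choice is expensive. At equal SDs and a correlation of 0.1, the test on change has 1.8 times the variance of the test on the 4-week value.

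The same gap affects the next trial. If the SD of change is carried forward where the residual SD would have served, that trial is sized too large.

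**Working it through.** **Inputs.** From the documents: N = 30, 1:1 allocation (15 per arm), markers at admission and 4 weeks. The sample is one of convenience, so there is no power calculation to reproduce. Assumed, because the documents give neither: r, the admission/4-week correlation, and k, the admission SD divided by the 4-week SD. Data are taken as near-normal, on the log scale if need be. The comparison is with t-tests, not with Mann-Whitney.

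**Formulas**, in units of the 4-week variance:
- 4-week value: 1
- change: 1 + k² − 2rk
- ANCOVA: (1 − r²) × (1 + 1/(N − 4)). At N = 30 the second factor is 1 + 1/26 = 1.0385, the average price of estimating the slope.

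**Largest cost.** The variance of change can be written (1 − r²) + (k − r)², which is never below 1 − r². The variance of the 4-week value, 1, is never below 1 − r² either. So at any r and k ANCOVA is at most 1.0385 times either one: 3.8% worse, reached at r = 0 (against the 4-week value) or k = r (against change). It also has 27 residual degrees of freedom instead of 28, which widens intervals by a factor of 1.0017. In squared width the worst case is 4.2%.

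**Equal SDs (k = 1), 30 complete pairs:**

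| r | 4-week | Change | ANCOVA | ANCOVA vs 4-week | ANCOVA vs change |
|---|---|---|---|---|---|
| 0.1 | 1 | 1.80 | 1.028 | 3% more | 43% less |
| 0.3 | 1 | 1.40 | 0.945 | 5% less | 32% less |
| 0.5 | 1 | 1.00 | 0.779 | 22% less | 22% less |
| 0.7 | 1 | 0.60 | 0.530 | 47% less | 12% less |

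Against the better of the two t-tests the gain peaks at r = 0.5: 1 − 0.75 × 1.0385 = 22%, an interval 0.88 times as wide. ANCOVA breaks even with the 4-week value at r = √(1 − 1/1.0385) = 0.19, and with change at r = 2/1.0385 − 1 = 0.93. Simulation (200,000 trials, 15 per arm) gave ratios to the better test of 1.037 at r = 0, 0.780 at r = 0.5 and 1.013 at r = 0.95.

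**Unequal SDs, against change:**

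| r | k = 0.5 | k = 0.7 | k = 1.5 |
|---|---|---|---|
| 0.3 | 0.945/0.95: 0.5% less | 0.945/1.07: 12% less | 0.945/2.35: 60% less |
| 0.5 | 0.779/0.75: 3.8% more | 0.779/0.79: 1% less | 0.779/1.75: 55% less |

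**Fewer complete pairs (k = 1).** The largest cost and largest gain become 5.0% and 21.3% at N = 24, 6.3% and 20.3% at N = 20, and 8.3% and 18.8% at N = 16.

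**Missing admission values.** The Subjects section says "Subjects will be enrolled within the first 36 hours of admission". Samples can only follow consent, so some may be missed. Assume 3 of 30, and compare with a 4-week t-test that keeps all 30. Complete-case ANCOVA is (30/27) × (1 + 1/23) × (1 − r²) = 1.159 × (1 − r²): 16% more variance at r = 0, 5.5% more at r = 0.3, 13% less at r = 0.5, with break-even at r = 0.37. If the missing covariate is filled with the mean of both arms pooled, all 30 stay in. Simulation then gives 4% more at r = 0, 4–5% less at r = 0.3 and about 19% less at r = 0.5.

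**Next trial.** At k = 1 the sample size from the SD of change is 2(1 − r)/(1 − r²) = 2/(1 + r) times that from the residual SD: 1.33 at r = 0.5 and 1.82 at r = 0.1.

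**The case against.** The strongest reply is that an adjusted analysis is already planned. The regression covers inflammation and the biopsy measures, and nothing excludes the admission value from it. If it is included, the treatment estimate is the same as from ANCOVA and nothing is gained. This stands: the gap is an unstated covariate list, not a missing model. The list is unstated for Aim 2 as well. There, however, the first assessment is at 14 days, after the NMES period, so it is not a pre-treatment covariate in the same sense.

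The outcomes are also worded as changes, which points to a test on change. If that is meant, a patient without an admission sample drops out of that test too, so the 16% penalty does not arise. This is fair. That figure applies only if the 4-week value is tested, which the plan neither names nor rules out.

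The 22% rests on equal SDs, which is doubtful when the first sample is taken during an exacerbation. This also stands as a limit. At k = 0.5 and r = 0.25, for example, the gain over the better t-test is only 1 − 0.9375 × 1.0385 = 3%. But 22% is not a ceiling when SDs differ. At k = 1.5 and r = 0.7 the change variance is 1.15, so the 4-week value is the better test, and ANCOVA at 0.530 has 47% less. The bound on the cost does not depend on k.

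Finally, skewed markers may be sent to Mann-Whitney, which these figures do not describe. The count of 3 missing is illustrative. The documents also do not say that the admission sample precedes randomisation, which the adjustment presumes.

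**Conclusion.** The concern holds, as an optional precision improvement to a secondary aim of a pilot. No Aim 3 analysis names the admission value as a covariate, although it is planned for every marker.

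With 30 complete pairs ANCOVA costs at most 3.8% in variance against either unadjusted t-test, whatever the correlation and SD ratio. At equal SDs it gains up to 22% over the better one, at r = 0.5. The correlation and the SD ratio are assumptions throughout. The gain can be close to nil when the admission SD is the smaller one, and well above 22% when it is the larger. It is zero against a regression that already includes the admission value. No bias is alleged, and the readmission outcome is untouched.

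**What to change.** For each Aim 3 marker, name as the main between-group comparison an ANCOVA of the 4-week value on arm and the admission value, both on the log scale where the marker is skewed, in place of the unadjusted test. If the regression on change is kept, list the admission value as a covariate; the treatment estimate is then the same.

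State whether the admission sample is taken before randomisation. Give a rule for missing admission values, for example the mean of both arms pooled, so that patients with a 4-week value stay in the model.

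Report the adjusted difference (or ratio) with its 95% CI, the residual SD and the admission/4-week correlation. Say which SD will size the next trial.

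The cost is a few lines of SAP text and no new measurements. The statistical price is one degree of freedom and up to about 4% more variance with complete pairs. Without the missing-value rule, the price against a 4-week test could reach about 16% (3 of 30 missing, r = 0).

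### The plan leaves the test for 30-day readmission open between chi-square and Fisher; at about 15 per arm neither sits well at the 5% level, and one named Boschloo test is a cheap improvement

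*Combined protocol and SAP*

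**What the plan says.** The opening paragraph of the combined protocol and SAP defines the endpoint: "The primary outcome is the rate of all-cause readmissions within 30 days following an index hospitalization for COPD exacerbation". The section on sample size and statistical considerations sets the size: "We propose enrolling a sample size of convenience of 30 participants randomized to intervention and usual care". The Protocol/Intervention section adds that patients "will be randomized in a 1:1 ratio to either receive remote tele pulmonary rehabilitation intervention or usual care". Together these imply about 15 per arm, but the documents do not state that number and describe no blocking.

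The statistical section compares groups "using chi-square or Fisher's exact test for categorical variables" and adds: "Comparisons will be deemed to be statistically significant at a two-tailed alpha of 0.05 or less". It assigns no separate test to the primary outcome, gives no expected-count threshold, and does not say whether chi-square carries a continuity correction. It does say what the primary result is for: "We will use the observed effects size for the primary outcome of 30-day readmission to design a larger clinical trial".

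**The concern.** In large samples the two named tests nearly coincide and leaving the choice open is harmless. At around 15 per arm they do not. Fisher's test works far below the declared 5% level and so loses power. Uncorrected chi-square can go above that level. Some plausible tables are significant by one and not by the other, so a reader could not tell whether the test was chosen before or after the counts were seen. What is at stake is the significance statement on the primary outcome, and some power in a trial that has little.

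**Working it through.** The plan states no power, event rate or effect size, so there is no figure of its own to reproduce.

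**Inputs.** From the documents: N = 30, 1:1 allocation, two-sided 0.05, chi-square or Fisher. Derived: 15 per arm. Assumed: each patient counts as readmitted or not; the readmission rates below are illustrative.

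**Method.** For arms of n1 and n2, list every table (a, b) of readmitted patients and compute each test's p-value. At a common rate π,

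size(π) = Σ Bin(a; n1, π) × Bin(b; n2, π), summed over tables with p ≤ 0.05.

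Maximum size is the largest value for π from 0.001 to 0.999. Power uses the same sum with different rates in the two arms. Boschloo's p-value takes Fisher's p as the ordering statistic and maximises the null probability of a table at least as extreme over π.

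**Step 1: one table by hand, 4/15 v 0/15.**
- Uncorrected chi-square: 30 × (4×15 − 0×11)² / (15×15×4×26) = 108,000 / 23,400 = 4.615, p = 0.032.
- Fisher: 2 × C(15,4) / C(30,4) = 2 × 1,365 / 27,405 = 0.100.
- Boschloo: 0.043.
- Yates-corrected chi-square: 0.107.
- Smallest expected count: 15 × 4 / 30 = 2.0.

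Likewise 6/15 v 1/15 gives 0.031, 0.080, 0.043 and 0.084, with smallest expected count 3.5. At 15/15 uncorrected chi-square is significant and Fisher is not for 0 v 4, 1 v 6, 2 v 7, 2 v 8, 3 v 9, 4 v 10 and their mirror images.

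**Step 2: maximum real size.**

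| Split | Fisher | Uncorrected chi-square | Boschloo |
|---|---|---|---|
| 15/15 | 1.8% | 5.5% | 4.3% |
| 14/14 | 2.1% | 5.2% | 4.2% |
| 14/15 | 2.8% | 6.2% | 4.4% |
| 14/16 | 3.1% | 5.9% | 4.6% |
| 13/17 | 2.9% | 5.4% | 4.9% |

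Yates-corrected chi-square at 15/15 has a maximum of 1.65%.

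**Step 3: power and disagreement at assumed rates of 30% v 10%.** With unequal arms the result depends on which arm has the higher rate, so both directions are shown. Disagreement is the chance that uncorrected chi-square and Fisher fall on opposite sides of 0.05.

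| n at 30% / n at 10% | Fisher | Boschloo | Gain (points) | Disagreement |
|---|---|---|---|---|
| 15/15 | 14.9% | 25.6% | 10.7 | 12.8% |
| 14/14 | 13.7% | 23.5% | 9.8 | 11.4% |
| 14/15 | 21.8% | 23.7% | 1.9 | 2.0% |
| 15/14 | 16.2% | 17.2% | 1.0 | 11.3% |
| 14/16 | 21.9% | 22.2% | 0.4 | 6.9% |
| 16/14 | 19.6% | 20.8% | 1.3 | 11.8% |
| 13/17 | 19.8% | 29.9% | 10.1 | 10.1% |
| 17/13 | 14.5% | 20.5% | 6.0 | 10.4% |

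Gains are taken before rounding. At every split listed, Boschloo rejects each table that Fisher rejects.

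**Step 4: the unwritten convention.** Suppose chi-square is used when every expected count is at least 5, and Fisher otherwise. At 15/15 that sends any table with fewer than 10 of 30 readmitted to Fisher, including 0 v 4, 1 v 6 and 2 v 7. The rule's real size is 1.9% at a common rate of 20%, 2.9% at 30% and 4.3% at 50%. Its power at 30% v 10% is 16.0%, against 14.9% for Fisher and 25.6% for Boschloo. At 20% v 10% the figures are 4.2%, 4.1% and 9.7%. The rule recovers more at higher rates: at 40% v 20% they are 16.0%, 11.2% and 19.2%.

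**The case against.** The case against giving this much weight is substantial, and several parts of it stand.

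- **The figures depend on the split.** A reader might infer that Fisher always runs below 2% here and that Boschloo always adds 10 points. The documents do not guarantee 15/15. A one-patient departure lifts Fisher's maximum to 2.8% and cuts the gain to 1 or 2 points. This stands.
- **The conflict needs two conditions.** A reader might infer that the verdict can be switched at will. That requires uncorrected chi-square and no expected-count convention. Yates-corrected chi-square agrees with Fisher at 15/15 on all but one table and its mirror (0 v 5, where Fisher gives 0.042 and Yates about 0.050). The usual convention settles both example tables in Step 1. This stands as a limit, but the plan states neither the correction nor the convention.
- **Fisher is not an error.** It keeps the error rate under 5%. Nor is it the weakest valid choice: at 15/15 Yates has 10.7% power at 30% v 10%, against Fisher's 14.9%.
- **This is a pilot of convenience size.** Its main product is the effect estimate, and no power is claimed. Boschloo does not change that: 26% power is still low. However, the plan declares a significance threshold, and Aim 1 asks whether readmissions are reduced, so a test result will be reported.
- **The link to this test is inferred.** The endpoint is called a rate and could be read as a count of readmissions. In that case the plan names no count method, and a definition is still needed.
- **Naming either listed test with a rule would also remove the ambiguity.** That is true, but at 15/15 and low readmission rates the usual rule leaves power close to Fisher's.

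**Conclusion.** The point holds in a limited form. The plan offers two tests for the outcome that matters most, with no rule for choosing between them. At about 15 per arm Fisher's largest real size is 1.8% to 3.1%, while uncorrected chi-square goes above 5% at every split checked. Boschloo's test stays below 5% and is never less powerful than Fisher's. At assumed rates of 30% v 10% it gains about 10 points at 15/15 and 14/14, 6 to 10 at 13/17, and 0 to 2 at 14/15 and 14/16.

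This rests on readmission being analysed as yes/no per patient, on arms near 15, and on assumed rates, because the documents give none. The disagreement figures of about 2% to 13% also assume uncorrected chi-square and a free choice of test. The documents do not support the stronger inference that the planned analysis is invalid or that the trial's conclusions hang on this choice. It is a cheap improvement to a low-powered pilot.

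**What to change.** In the statistical section:

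1. Define the primary outcome as the proportion of patients with at least one all-cause readmission within 30 days.
2. Replace the two-test wording, for this outcome, with one prespecified two-sided Boschloo exact test at the 5% level.
3. Report the risk difference with a score or exact unconditional 95% confidence interval as the main result. The interval shows how uncertain the effect carried into the larger trial is.

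The cost is two or three sentences and a standard software function, with no extra patients or data. The drawback is that Boschloo's test is less familiar to readers than Fisher's.
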